#### **5.4.3. Adverse Events**

Adverse events (AEs) will be coded using the Medical Dictionary for Regulatory Activities (MedDRA) version 27.0 or higher.

An AE will be considered as a treatment-emergent adverse event (TEAE) if the AE began or worsened (increased in severity or became serious) on or after the date of the first dose of open-label study treatment. An AE that occurs more than 30 days after the last dose of open-label study treatment or the safety follow-up visit (Visit 15) in this extension study whichever comes later will not be counted as a TEAE. Per case report form instructions, a new AE record will be created for any AE that worsens; therefore, TEAEs can be identified as those AEs captured in Study 3101-306-002 with recorded onset date on or after the date of the first dose of open-label study treatment and within 30 days after the last dose of open-label study treatment or Visit 15 whichever comes later.

An AE is a TESAE if it is a TEAE that additionally meets any SAE criterion below (as specified in the protocol Section 9.1.2):

- Results in death
- Is life threatening
- Requires inpatient hospitalization or prolongation of existing hospitalization
- Results in persistent disability/incapacity
- Is a congenital anomaly/birth defect
- Other situations that the medical or scientific judgment considers to be serious.

TEAEs that started after the date of last dose of open-label study treatment will be considered as newly emergent TEAEs (NEAEs).

TEAEs that started on or after the date of first dose of open-label study treatment will be summarized.

Overall summary of AEs will be provided on a per-participant basis for categories of TEAEs, treatment-related TEAEs, TESAEs, treatment-related TESAEs, TEAEs leading to study intervention discontinuation, and deaths.

The number and percentage of participants reporting TEAEs will be tabulated by system organ class (SOC) and preferred term (PT), and further categorized by severity. If more than 1 AE is coded to the same preferred term for the same participants, the participant will be counted only once for that preferred term using the greatest severity for the summarization by severity.

The number and percentage of participants reporting treatment-related TEAEs will be tabulated by SOC and PT.

The number and percentage of participants reporting treatment-related TEAEs will be tabulated by SOC, PT, and the following AE onset time intervals: < 3 months,  $\geq$  3 and < 6 months,  $\geq$  6 and < 9 months,  $\geq$  9 and < 12 months,  $\geq$  12 months, where a month is defined as 30 days for analysis purposes.

The number and percentage of participants reporting NAEs will be tabulated by SOC and PT.

The number and percentage of participants who have TEAEs leading to study intervention discontinuation will be summarized by SOC and PT.

The incidence of common ( $\geq$  2% of participants [after rounding] in either CM completer cohort or De Novo EM cohort) TEAEs will be summarized by PT and sorted by decreasing frequency in total.

The incidence of common ( $\geq$  5% of participants [after rounding] in either CM completer cohort or De Novo EM cohort) TEAEs will be summarized by PT and sorted by decreasing frequency in total.

The number and percentage of participants who have TESAE will be tabulated by SOC and PT.

The number and percentage of participants reporting treatment-related TESAEs will be tabulated by SOC and PT.

In addition, separate tabular displays will be presented for participants who died, participants with SAEs, and participants with TEAEs leading to study intervention discontinuation.

#### **5.4.4. Additional Safety Assessments**

##### **5.4.4.1. Clinical Laboratory Parameters**

Descriptive statistics for values and changes from the baseline in standard (SI) units at each assessment time point will be presented for the following laboratory parameters:

Category	Parameter
Chemistry	Sodium, potassium, chloride, bicarbonate, glucose, blood urea nitrogen, creatinine, total bilirubin, alkaline phosphatase, aspartate aminotransferase, alanine aminotransferase, lactate dehydrogenase, creatine kinase, total protein, albumin, calcium, phosphorus, uric acid, total cholesterol, the estimated glomerular filtration rate
Hematology	Hemoglobin, hematocrit, red blood cell count, red blood cell indices (mean corpuscular volume, mean corpuscular hemoglobin, mean corpuscular hemoglobin concentration), white blood cell count, including differential (neutrophils, lymphocytes, monocytes, eosinophils, and basophils), platelet count
Urinalysis	Specific gravity, pH

In addition, descriptive statistics for values and changes from the baseline values in conventional units at each assessment time point will be presented for selected clinical laboratory parameters listed in [Table 6-1](#). A description of reporting the laboratory values in conventional units in participant narratives (along with the standard reporting in SI units) is presented at the end of [Table 6-2](#).

Clinical laboratory test values will be considered potentially clinically significant (PCS) if they meet either the lower-limit or higher-limit PCS criteria listed in Section [6.3.7.2](#). The number and percentage of participants who have PCS postbaseline clinical laboratory values will be tabulated. The percentages will be calculated relative to the number of participants with available non-PCS baseline values and at least 1 postbaseline assessment for the open-label treatment period. The numerator will be the total number of participants with available non-PCS baseline values and at least 1 PCS postbaseline value during the study. A supportive tabular display of participants with PCS values will be provided.

In addition, a tabular display showing all AEs that occurred in participants who had PCS postbaseline clinical laboratory values will be provided.

The number and percentage of participants with an adjudicated case (i.e.,  $ALT \geq 3 \times ULN$  and/or  $AST \geq 3 \times ULN$ ) will be summarized by relationship of ALT or AST elevation to study treatment. The percentages will be calculated relative to the number of participants with at least 1 adjudicated case. The numerator will be the number of participants with at least 1 adjudicated case in the specific category of relationship. If a participant has more than 1 adjudicated case, he or she will be counted in the most relevant category of relationship.

Participants with an adjudicated case (i.e.,  $ALT \geq 3 \times ULN$  or  $AST \geq 3 \times ULN$ ) will be listed with their ALT and AST assessments, adjudication dates, relationship of ALT or AST elevation to study treatment, and confounding factor(s). Additional listings will be provided for

participants who meet  $ALT \geq 3 \times ULN$  or  $AST \geq 3 \times ULN$  and/or potential Hy's law and have one of the following categories: at least 1 abnormal liver biochemistry risk factor, at least 1 liver disease sign and symptom, at least 1 liver diagnostic test performed, consultation with a specialist for liver evaluation, liver lab tests performed, and drug screen performed, respectively.

Potential Hy's Law criteria is defined by a postbaseline elevation of alanine aminotransferase (ALT) or aspartate aminotransferase (AST)  $\geq 3 \times ULN$ , along with total bilirubin (TBL)  $\geq 2 \times ULN$  and a non-elevated alkaline phosphatase (ALP)  $< 2 \times ULN$ , all based on blood draws collected within a 24-hour period. Participants who meet the potential Hy's Law criteria from the first dose of study treatment to the end of study will be summarized. Supportive tabular displays will also be provided.

The number and percentage of participants meeting each of the postbaseline hepatic laboratory abnormalities criteria listed in [Table 6-4](#) will be summarized. The percentages will be calculated relative to the number of participants with at least 1 available postbaseline assessment. The numerator will be the total number of participants having at least 1 postbaseline value that meets the specific category during the study. A supportive listing will also be provided.

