Japanese participants with EM will be newly recruited at selected sites only. Participation will begin with a 4-week screening/baseline period starting at Visit -1. Participants who complete the 4-week screening/baseline period and meet all entry criteria will be enrolled into the 52-week open-label treatment period at Visit 1.

For all participants, after Visit 1 study visits will occur every 4 weeks for the duration of the 52-week treatment period. Participants will return to the clinic for safety assessments at 4, 8, 12, 16, 20, 24, 28, 32, 36, 40, 44, 48, and 52 weeks relative to Visit 1 (Day 1). An EOS visit will occur 4 weeks after the last dose of atogepant 60 mg once daily. For details, please see [Table 1](#), Schedule of Visits and Procedures.

The primary objective of the study is to assess the long-term safety and tolerability of atogepant treatment in Japanese participants. The planned safety assessments include collection of AEs,

clinical laboratory determinations, ECGs, vital sign measurements, physical examinations, and the C-SSRS.

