8.4.3 Safety Follow-up Period (4 Weeks)

8.4.3.1 Visit 15/End of Study (Week 56)

- Prior to any other test or evaluations, administer the following PRO measures: HIT-6, EQ-5D-5L and MSQ v2.1.
- Perform physical examination.
- Collect vital sign measurements (sitting and standing systolic and diastolic BP, sitting and standing pulse rate, respiration rate, temperature, and weight).
- Perform urine pregnancy test for women of childbearing potential.
- Collect blood and urine samples for chemistry, hematology, INR, and urinalysis.
- Assess C-SSRS (the “Since Last Visit” assessment of the C-SSRS will be completed).
- Review and assess AEs.
- Update concomitant medications and concurrent procedures.
- Access IWRS to enter study visit.

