**Table 6-10 Safety Analysis Visit Definitions**

Analysis Phase	Analysis Visit (Derived)	Scheduled Study Visit (eCRF)	Window
Pretreatment	Baseline	Visit 1 for De Novo EM Participant only	Baseline from lead-in study for 3101-303-002 Completer Treatment Day $\leq 1$ for De Novo EM Participant
Open-label Treatment Period	Week 4	Visit 2	Treatment Day [1, 42] for 3101-303-002 Completer Treatment Day [2, 42] for De Novo EM Participant
	Week 8	Visit 3	Treatment Day [43,70]
	Week 12	Visit 4	Treatment Day [71,98]
	Week 16	Visit 5	Treatment Day [99,126]
	Week 20	Visit 6	Treatment Day [127,154]
	Week 24	Visit 7	Treatment Day [155,182]
	Week 28	Visit 8	Treatment Day [183,210]
	Week 32	Visit 9	Treatment Day [211,238]
	Week 36	Visit 10	Treatment Day [239,266]
	Week 40	Visit 11	Treatment Day [267,294]
	Week 44	Visit 12	Treatment Day [295,322]
	Week 48	Visit 13	Treatment Day [323,350]
	Week 52	Visit 14/ET	Treatment Day $\geq 351$ and within open-label treatment period
	End of treatment		Last available assessment during open-label treatment period
Safety Follow-up Period	Week 56 (Safety follow-up)	Visit 15	Treatment Day [the end of open-label treatment period +1, the last study visit]
	End of study		Last available assessment after treatment start date, i.e., occurs at final visit (expected Day 392) or ET

ET = early termination

Safety follow up visit will be presented in analysis tables for clinical laboratory values and vital signs.

End of Open label Treatment is defined as the last available assessment during open label treatment period. End of Open label Treatment results will be presented in analysis tables for clinical laboratory values, electrocardiograms and vital signs.

End of Study is defined as the last available assessment during the study, including open label and safety follow up period. End of Study results will be presented in analysis tables for safety parameters, including but not limited to clinical laboratory values, and vital signs.

For endpoints collected by visit, the last visit with a non-missing value will be used for analysis, if a participant has 2 or more visits within the same window.

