#### **6.4.4. Repeated or Unscheduled Assessments of Safety Parameters**

Baseline is defined as the last assessment made before the first dose of study treatment. If end-of-study assessments are repeated or if unscheduled visits occur, the last non-missing postbaseline assessment will be used as the end-of-study assessment for generating summary statistics. However, all postbaseline assessments will be used for PCS value determinations, and all assessments will be presented in the data listings.

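### The laboratory PCS percentage in SAP 5.4.4.1 has an open-label denominator and a whole-study numerator, so it is neither an open-label rate nor a whole-study rate

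*SAP*

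**What the plan says.** SAP 5.4.4.1 defines the percentage in two adjacent sentences. The denominator is the number of participants "with available non-PCS baseline values and at least 1 postbaseline assessment for the open-label treatment period". The numerator is the number with "available non-PCS baseline values and at least 1 PCS postbaseline value during the study"; it carries no requirement for an open-label sample.

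Three other places fix what the numerator covers:

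- SAP 6.4.4 states that "all postbaseline assessments will be used for PCS value determinations", with no cut-off at the last dose.
- The notes to SAP Table 6-10 say "End of Study is defined as the last available assessment during the study, including open label and safety follow up period". The same table gives Week 56 its own Safety Follow-up Period, starting the day after the open-label period ends.
- Protocol 8.4.3.1 has sites take laboratory samples at Visit 15 ("Collect blood and urine samples for chemistry, hematology, INR, and urinalysis"), and Protocol 3.1 sets the timing: "An EOS visit will occur 4 weeks after the last dose of atogepant 60 mg once daily".

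The neighbouring rules differ. The hepatic-abnormality rule (end of SAP 5.4.4.1), the vital-sign rule (5.4.4.2) and the ECG rule (5.4.4.3) also count values over the whole study, but none limits its denominator to the open-label period. SAP 5.5.1 has all safety endpoints shown by cohort as well as overall.

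**The concern.** A proportion is interpretable when both halves refer to the same participants over the same period. Here a Week 56 value can put a participant in the numerator but can never qualify anyone for the denominator. The result cannot be labelled as an open-label rate or as a whole-study rate. The numerator is also not guaranteed to be a subset of the denominator, so two programmers could handle the odd case differently and both claim to follow the SAP.

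Safety is the primary objective, and this is one of its laboratory tables. The stake is a clear, reproducible definition. No test or error rate depends on it, because the SAP specifies no hypothesis.

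**Working it through.** **1. Periods side by side**

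| SAP rule | Denominator sample from | Numerator value from |
|---|---|---|
| Laboratory PCS (5.4.4.1) | open-label period | whole study |
| Hepatic abnormalities (5.4.4.1) | any postbaseline | whole study |
| Vital-sign PCS (5.4.4.2) | any postbaseline | whole study |
| ECG PCS (5.4.4.3) | any postbaseline | whole study |

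Only the first row is mismatched.

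**2. Who can be in the numerator but not the denominator**

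The participant needs a non-PCS baseline, no open-label sample and a PCS value at Week 56.

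- *Rollovers (at least 140).* Under SAP 5.1 their baseline is the lead-in value, and Table 6-10 opens their first window on Day 1. The Visit 1 sample already counts as an open-label assessment, so the case hardly arises.
- *De Novo (about 30).* Their Day 1 sample is baseline and their window opens on Day 2. They would need no sample from Day 2 to the end of the open-label period, including Visit 14/ET, and then a sample at Visit 15. Protocol 8.4.4 caps remote visits at 8 weeks and has missed samples collected at the next in-person visit, so this should be rare. An early stopper whose ET sample is classed as after the open-label period is the likeliest route.

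**3. Size of the Week 56 contribution**

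The documents give no PCS rate, so there is no planned figure to reproduce. Inputs:

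- Scheduled postbaseline laboratory visits: Weeks 4 to 52 = 13 open-label, plus Week 56 = 14. Share off treatment: 1/14 = 7.1%.
- Planned size: 140 + 30 = 170 (SAP section 3).
- Assumed: probability p of a PCS value per sample for one parameter, independent between visits, full attendance.

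Formulas: open-label only, 1 − (1 − p)^13; with Week 56, 1 − (1 − p)^14.

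| p | Weeks 4–52 | plus Week 56 | difference (points) | participants of 170 |
|---|---|---|---|---|
| 0.1% | 1.29% | 1.39% | 0.10 | 0.17 |
| 0.5% | 6.31% | 6.78% | 0.47 | 0.80 |
| 1% | 12.25% | 13.13% | 0.88 | 1.49 |
| 2% | 23.10% | 24.64% | 1.54 | 2.61 |

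For a participant who stops after one open-label sample, p = 1% gives 1.00% against 1 − 0.99² = 1.99%, so Week 56 weighs more for early terminators. If PCS values persist within a participant, the extra sample adds less than the table shows, and nothing if persistence is complete.

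**4. De Novo column**

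One participant is 1/30 = 3.3 points. Suppose 1 of 30 has no open-label sample but a PCS value at Week 56, and nobody else has a PCS value:

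- rule as written: 1/29 = 3.45%
- both halves open-label: 0/29 = 0%
- both halves whole-study: 1/30 = 3.33%

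**The case against.** The strongest reply is that whole-study counting is plainly intended. SAP 6.4.4 and the three sibling rules all work that way. SAP 5.4.3 counts adverse events as treatment-emergent up to 30 days after the last dose or Visit 15, whichever is later, so a Week 56 value sits inside that window too. On this view the fault is a stray phrase in one denominator. That is largely right, and it decides which fix is simplest. It does not make the rule as written coherent.

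A reader might go further and infer that off-drug values contaminate an on-treatment percentage and inflate it. The documents do not support that: the SAP never calls this table on-treatment, and only its denominator is tied to the open-label period.

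A reader might also infer that abnormalities first seen after stopping are hidden. They are not. SAP 5.4.4.1 plans a supportive display of participants with PCS values, 6.4.4 puts every assessment in the listings, and the notes to Table 6-10 have the follow-up visit shown in the laboratory tables. It is only the summary percentage that does not separate them. The SAP does separate periods elsewhere: adverse events starting after the last dose (5.4.3) and C-SSRS responses (5.4.4.4).

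Finally, the laboratory events of special interest, ALT/AST elevations and potential Hy's law cases, have their own summaries, and the hepatic table has no mismatch. That stands and keeps the point minor.

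**Conclusion.** The point holds as an internal inconsistency in one stated rule. The laboratory PCS percentage mixes two periods, and its numerator need not lie inside its denominator, although the second fault should be rare and nearly confined to De Novo participants. The overall effect is probably about one percentage point or less per parameter. That rests on assumed, independent per-sample risks of up to 1% and full attendance; it reaches about 1.5 points at 2% and shrinks with within-participant persistence. The small De Novo column is more sensitive. This is a minor correction to a descriptive table, with no bearing on any hypothesis or decision threshold.

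**What to change.** Put both halves on one period.

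- *Simplest.* In SAP 5.4.4.1, strike the closing words of "at least 1 postbaseline assessment for the open-label treatment period" that limit the assessment to the open-label period. The rule then agrees with 6.4.4 and with the hepatic, vital-sign and ECG rules. Add a count of participants whose first PCS value falls in the safety follow-up period, among those with a follow-up sample.
- *Alternative.* Limit both numerator and denominator to the open-label period, tabulate follow-up separately, and amend 6.4.4 to agree. Limiting the numerator alone would conflict with 6.4.4 as it stands and put this table on a different basis from its siblings.

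Either way, state how the end of the open-label period is dated, since Table 6-10 uses that boundary without defining it and the classification of an ET sample depends on it. The cost is SAP wording and one extra column; no new data are needed.

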#### 5.4.4.2. Vital Signs

Descriptive statistics for vital signs (systolic and diastolic blood pressures [sitting and standing], pulse rate [sitting and standing], respiratory rate, temperature, weight, body mass index (BMI), orthostatic systolic blood pressure, orthostatic diastolic blood pressure, and orthostatic pulse rate) and their changes from baseline at each assessment timepoint will be presented. Orthostatic vital sign values (orthostatic systolic and diastolic blood pressures, and orthostatic pulse rate) are defined as the corresponding standing measurement minus sitting measurement of systolic and diastolic blood pressures and pulse rate respectively.

Vital sign values will be considered PCS if they meet both the observed value criterion and the change from baseline value criterion, if both criteria are available, or meet either the observed value criterion or the change from baseline value criterion that will be detailed in [Section 6.3.7.4](#). The number and percentage of participants who have PCS postbaseline vital sign values will be tabulated. For criteria related with systolic blood pressure, diastolic blood pressure, pulse rate and weight, the denominator will be the number of participants who have available baseline and at least 1 postbaseline assessment. For criteria related with orthostatic measures, the denominator will be the number of participants who have available non-PCS baseline and at least 1 postbaseline assessment. The numerator will be the total number of participants with at least 1 PCS postbaseline value during the study. A supportive listing of PCS values will be provided.

In addition, a tabular display showing all AEs that occurred in participants who had PCS postbaseline vital sign values will be provided.

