## 5. Statistical Analyses

### 5.1. General Considerations

- Efficacy endpoints will be analyzed descriptively based on the mITT population.
- Safety endpoints will be performed using the Safety population.
- Continuous variables will be summarized by number of participants with observed values (n), mean, standard deviation (SD), median, 1st and 3rd quartiles (Q1, Q3), minimum (min), and maximum (max).
- Categorical variables will be summarized by number of participants with observed values, events (n), frequency count (n1), and percentage of participants with observed values.
- Partial dates will be treated as missing in computation or in variable derivation unless specified otherwise, but will be listed in the data listings as they appear on the eCRF.
- For monthly endpoints, baseline is defined as assessments during the last 28 days of baseline period in the lead-in study for 3101-303-002 rollover participants, and the last 28 days of the screening/baseline period for De Novo EM Participants. For efficacy endpoints that are assessed at clinical visits, baseline is defined as the last non-missing efficacy assessment before the first dose of study intervention in the lead-in study (3101-303-002) for 3101-303-002 Completers, and the last non-missing efficacy assessment before the first dose of study for De Novo EM Participants. For each of the clinical, laboratory, vital sign, and ECG parameters, the baseline is defined as the baseline value in the lead-in study (3101-303-002) for 3101-303-002 Completers, and the last nonmissing safety assessment before the first dose of study drug for De Novo EM Participants.
- The change from baseline values will be computed as the post-baseline value minus the baseline value.
- Study intervention is treatment administered (atogepant 60 mg QD).
- All statistical analysis will be performed using SAS version 9.4 or higher.
- Medical Dictionary for Regulatory Activities (MedDRA), Version 27.0 or higher, will be used to code adverse events and medical history.
- WHO Drug Global B3 (v.202403 or higher) will be used to code medications.

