#### **5.4.4.3. Electrocardiogram**

Descriptive statistics for ECG parameters (i.e., heart rate, PR interval, QRS interval, RR interval, QT interval, and QTc interval) and changes from baseline values at each assessment timepoint will be presented. The QTc will be calculated using the Fridericia correction.

ECG parameter values are considered PCS if ECG values meet either the actual value or change from baseline PCS high criteria listed in [Table 6-5](#). The number and percentage of participants with PCS postbaseline values will be tabulated. The percentages will be calculated relative to the number of participants with an available non-PCS baseline value and at least 1 postbaseline assessment. The numerator will be the total number of participants with an available non-PCS baseline value and at least 1 PCS postbaseline ECG value during the study. A supportive listing of participants with PCS postbaseline values will be provided. A listing of all AEs for participants with PCS ECG values will also be provided.

To evaluate ECG postbaseline values of clinical interest, the number and percentage of participants with post-treatment QTcF  $> 450$  msec,  $> 480$  msec, and  $> 500$  msec will be tabulated. A supportive listing of participants with postbaseline clinical interest will be provided. A listing of all AEs for participants with postbaseline clinical interest will also be provided.

The number and percentage of participants with an increase  $> 30$  msec but  $\leq 60$  msec, and with an increase  $> 60$  msec in QTcF will be tabulated. Participants will be counted only once for the most severe category. A supportive listing of participants with postbaseline QTcF increases  $> 30$  msec will be provided, including the PID number and all QTc values (including changes from baseline). A listing of all AEs for participants with postbaseline QTcF increases  $> 30$  msec will also be provided.

A shift table from baseline to the end of open-label treatment period in the investigator's overall interpretation of the ECG will be presented for the following categories: normal; abnormal, not clinically significant; abnormal, clinically significant. A tabular display of participants with postbaseline clinically significant ECG abnormalities according to the investigator's overall interpretation will be provided.

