#### Safety Subgroup Analyses

For all safety endpoints, subgroup analyses will be performed by 3101-303-002 Completers or De Novo EM Participants and overall.

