#### 6.3.7.4. Potentially Clinically Significant Criteria for Vital Signs

**Table 6-5 Potentially Clinically Significant Criteria for Vital Signs**

Parameter	Flag	Criteria	
		Observed Value	Change from Baseline
Systolic blood pressure, mm Hg	High	$\geq 180$	Increase of $\geq 20$
	Low	$\leq 90$	Decrease of $\geq 20$
Diastolic blood pressure, mm Hg	High	$\geq 105$	Increase of $\geq 15$
	Low	$\leq 50$	Decrease of $\geq 15$
Pulse rate, bpm	High	$\geq 120$	Increase of $\geq 15$
	Low	$\leq 50$	Decrease of $\geq 15$
Weight, kg	High	—	Increase of $\geq 7\%$
	Low	—	Decrease of $\geq 7\%$
Orthostatic SBP change, mm Hg	Low	$\leq -20$	—
Orthostatic DBP change, mm Hg	Low	$\leq -15$	—
Orthostatic Pulse rate change, bpm	High	$\geq 25$	—

SBP = Systolic blood pressure; DBP = Diastolic blood pressure; bpm = beats per minute

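### SAP 5.4.4.2: the orthostatic PCS numerator omits the non-PCS-baseline condition of its denominator, so the percentage as written may not be a true proportion

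*SAP*

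**What the plan says.** SAP 5.4.4.2 (Vital Signs) sets two denominators for the PCS percentages. For systolic and diastolic blood pressure, pulse rate and weight, a participant needs a baseline, PCS or not, and at least one later assessment. For the orthostatic measures the rule is stricter: "the denominator will be the number of participants who have available non-PCS baseline and at least 1 postbaseline assessment". A single numerator sentence then serves both groups: "The numerator will be the total number of participants with at least 1 PCS postbaseline value during the study".

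Other parts of the SAP that bear on this:

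- **Table 6-5** has three orthostatic rows, the first being "Orthostatic SBP change, mm Hg" and the others diastolic pressure and pulse rate. Each has a threshold on the observed value (−20 mm Hg or lower, −15 mm Hg or lower, 25 bpm or higher) and no change-from-baseline criterion.
- **Section 6.4.4** states that "all postbaseline assessments will be used for PCS value determinations" and adds no baseline filter.
- **Section 5.1** fixes the reference point for vital signs: "the baseline is defined as the baseline value in the lead-in study (3101-303-002) for 3101-303-002 Completers". For De Novo EM participants it is the last nonmissing value before the first dose.
- **Section 5.4.4.1** (laboratory) pairs a non-PCS-baseline denominator with a numerator that matches it: "The numerator will be the total number of participants with available non-PCS baseline values and at least 1 PCS postbaseline value during the study".
- **Section 5.4.4.3** (ECG) does the same, counting "participants with an available non-PCS baseline value and at least 1 PCS postbaseline ECG value during the study".
- **Section 5.5.1** sets the display: "For all safety endpoints, subgroup analyses will be performed by 3101-303-002 Completers or De Novo EM Participants and overall".

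**The concern.** A percentage is a proportion only if everyone in the numerator is also in the denominator. For the orthostatic rows the written rule does not ensure that. Someone whose standing-minus-sitting difference already met the threshold at baseline is removed from the denominator, yet adds one to the numerator if the threshold is met again at any later assessment. The same holds for someone with no baseline value.

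The restricted denominator suggests that the row is meant to show orthostatic abnormalities that were not there at the start. Pre-existing findings would then inflate a rate that reads as new onset. Safety is the primary objective and there is no control arm, so these descriptive rates are read directly. Two programmers could also follow the section in good faith and report different figures.

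**Working it through.** The documents state no figure on this point, so there is nothing to reproduce. The check compares the definitions and then sizes the effect.

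**1. Numerator and denominator compared**

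| SAP section | Baseline condition in denominator | Baseline condition in numerator | Numerator inside denominator? |
|---|---|---|---|
| 5.4.4.1 Laboratory PCS | available, non-PCS | available, non-PCS | yes |
| 5.4.4.3 ECG PCS | available, non-PCS | available, non-PCS | yes |
| 5.4.4.2 SBP, DBP, pulse rate, weight | available | none stated | yes, because every criterion needs a change from baseline |
| 5.4.4.2 Orthostatic SBP, DBP, pulse rate | available, non-PCS | none stated | not ensured |

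Only the orthostatic rows fail. Their criteria rest on the observed value, so they can be met at baseline and again later, or met with no baseline at all.

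**2. Whether the case can arise.** The blood pressure exclusion (Protocol 4.4.1, criterion 4) uses sitting values, and no listed entry criterion sets a limit on orthostatic change. Sitting and standing measurements are scheduled at every visit (Protocol 6.1.4), which gives up to 14 postbaseline visits (Visits 2 to 15).

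**3. Formula.** Let

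- D = stated denominator (non-PCS baseline and at least one later assessment),
- n = participants in D with a PCS postbaseline value,
- c = participants with a PCS or missing baseline who have a PCS postbaseline value.

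Matched percentage = n/D. As written = (n + c)/D. Excess = c/D, which is zero when c = 0 and never negative.

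**4. Size at the planned cohort sizes.** SAP section 3 plans about 30 De Novo EM participants, at least 140 Completers and at least 170 overall. The values of c are assumptions. D = N − c assumes that everyone else qualifies for the denominator.

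| c | De Novo EM (N = 30) | Completers (N = 140) | Overall (N = 170) |
|---|---|---|---|
| 0 | 0 | 0 | 0 |
| 1 | 1/29 = 3.4 points | 1/139 = 0.7 points | 1/169 = 0.6 points |
| 2 | 2/28 = 7.1 points | 2/138 = 1.4 points | 2/168 = 1.2 points |

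**5. Effect on a whole row.** Take N = 170, b participants PCS at baseline, a share r of them PCS again afterwards, and new PCS values in 5% of the rest. All of these except N are assumed. The matched value is 5.0% throughout. As written it is (0.05 × (170 − b) + r × b)/(170 − b):

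- b = 2: from 9.0/168 = 5.4% (r = 0.3) to 10.0/168 = 6.0% (r = 0.8)
- b = 5: from 9.75/165 = 5.9% to 12.25/165 = 7.4%
- b = 10: from 11/160 = 6.9% to 16/160 = 10.0%

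The limiting case shows that the ratio is not bounded. If all 170 had a PCS postbaseline value and b = 10, it would be 170/160 = 106.25%.

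**The case against.** The strongest reply is that a sensible programmer would read the numerator as restricted to the stated denominator. One sentence serves two denominators, so it could not easily repeat two different baseline conditions. The laboratory and ECG sections each have only one denominator for their PCS percentages, which weakens the contrast with them. SAP section 1 places table specifications in a separate document, which may already apply the restriction. This limits the claim to the rule as written. It does not remove the mismatch, because no other SAP text supplies the missing condition, and the SAP states it explicitly in the two parallel sections.

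The size is also entirely assumed, and that stands: the documents give no rate of orthostatic PCS values before or after treatment starts. Nothing supports c = 2 in the De Novo EM cohort in particular. The missing-baseline route is unlikely there too, since both Visit -1 and Visit 1 must be onsite and both include sitting and standing measurements. For Completers, baseline completeness depends on lead-in data that the documents do not show.

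Finally, the consequence is small. The rows are descriptive, the study tests no hypothesis, counts are shown beside percentages, and PCS values are listed. Also, the SAP does not itself call the row an incidence of new findings; that is inferred from the denominator. These points support a minor rating. They do not make the written rule consistent.

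**Conclusion.** The concern holds, as a minor point. Read literally, SAP 5.4.4.2 lets participants outside the orthostatic denominator enter its numerator, so the reported percentage can only equal or exceed the matched one. The excess is c/D. With one such participant it is 3.4 points in the De Novo EM cohort, 0.7 in Completers and 0.6 overall, assuming planned enrolment and that everyone else qualifies for the denominator. The true c is unknown and may be zero. The mismatch in wording is certain; an effect on the reported tables is not, because the table specifications are not available. Only the three orthostatic criteria are affected, in the cohort and overall displays. The percentages for blood pressure, pulse rate and weight are sound.

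**What to change.** In SAP 5.4.4.2, give the orthostatic criteria their own numerator: participants who have a baseline that is available and not PCS, and who have one or more PCS values afterwards. This is the condition already used in 5.4.4.1 and 5.4.4.3. Keep the present numerator for blood pressure, pulse rate and weight. A shorter alternative is to say once that each vital sign numerator is counted within its corresponding denominator. Check that the table specifications agree.

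The cost is one sentence and one filter in the program. The drawback is that later PCS values in participants who were PCS at baseline leave the percentage. They still feed the by-visit descriptive statistics but cannot be identified as PCS cases there, so the planned supportive listing of PCS values should explicitly retain them.
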